##### 3.1.3 As treated set (AT)

The AT population is defined the same as the m-ITT population but will be analyzed based on the actual treatment received.

##### 3.1.4 Per-protocol set (PPS)

The PPS population includes subjects in the m-ITT population who did not experience any significant protocol deviations, as determined by the sponsor.

##### 3.1.5 Safety analysis set (SS)

The SS population includes all subjects who received either IVT followed by EVT or EVT alone treatment and had at least one safety follow-up.

### 3.2 General principles of statistical analysis

#### 3.2.1 Analysis software and data transfer standards

Sample size calculation and statistical analyses will be performed using SAS 9.4 (or a later version). Analysis datasets will be generated following CDISC standards (SDTM Implementation Guide Version 3.2 and ADaM Implementation Guide Version 1.1). Statistical tables, figures, and listings will be generated in RTF file format.

#### 3.2.2 Reporting standards for analysis results

The ITT, m-ITT, and PPS datasets will be analyzed according to the randomized treatment groups, while the AT and SS datasets will be analyzed based on the actual interventions received. Issues related to cases or data handling not explicitly described in the clinical trial protocol will be resolved following case discussions.

Continuous variables will be described using the mean, standard deviation, median, quartiles, minimum, and maximum values. Categorical and ordinal data will be summarized using frequencies and percentages. Statistical measures and the number of decimal places will be reported as outlined in the table below:

Name	Description	Decimal Places (dp)
Quantitative Data		
N	Number of subjects without missing results	0 dp
Mean	Arithmetic mean	Raw data decimal places + 1 dp

SD	Standard deviation	Raw data decimal places + 1 dp
Median	Median value	Raw data decimal places
Q1	25th percentile (first quartile)	Raw data decimal places
Q3	75th percentile (third quartile)	Raw data decimal places
Min	Minimum value	Raw data decimal places
Max	Maximum value	Raw data decimal places
Missing	Number of missing cases	0 dp; if the percentage frequency is less than 0.1%, the percentage will be displayed to the first non-zero digit. For example, if the percentage is "0.000523%", it will be displayed as "0.0005%" instead of "0.0%".
Qualitative (Categorical and Ordinal) data		
n	Number of subjects with a specific evaluation indicator value	0 dp
%	Percentage (0-100%)	1 dp
Statistical measures		
95% CI	95% confidence interval	Raw data decimal places + 2 dp

The comparison of baseline characteristics between the two groups will be conducted using appropriate statistical methods according to the type of data. For quantitative variables, an independent samples t-test will be used if normality and homogeneity of variance are satisfied; otherwise, the Wilcoxon rank-sum test will be applied. For categorical data, a chi-square test will be used if all expected cell counts are  $\geq 5$ , a continuity-corrected chi-square test will be used if one expected cell count is between 1 and 5, and Fisher's exact test will be applied if more than one expected cell count is between 1 and 5, or if any expected cell count is  $< 1$ . For ordinal data, the Wilcoxon rank-sum test will be used without adjusting for center effects, while the Cochran-Mantel-Haenszel (CMH) test will be applied if adjustments for center effects are needed.

Unless otherwise specified, all statistical tests will be two-sided, with a significance level of 0.05 (two-sided). P-values will be reported to three decimal places, and values less than 0.001 will be reported as "P < 0.001".

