5.3 Rescue medications

If deemed necessary by the interventionalist, the use of local (intra-arterial) rtPA is permitted for all patients enrolled in BEST-BAO. The SC recommends that rtPA be given as a 5 mg bolus at a 5–10 min interval (maximum 40 mg) and that vascular patency be checked after each bolus. Patients who have already received IVT should not be administered more than 30 mg of intra-arterial rtPA during the EVT.

For patients in the EVT alone group who do not achieve successful reperfusion (defined as eTICI 2b–3) within the 4.5-hour time window and do not achieve the maximum rtPA dose, they may subsequently receive IVT with rtPA at a dose of 0.9 mg/kg. The total amount of rtPA for IVT received before and after EVT should not exceed the dose specified in the guidelines.

6. Investigational products

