### 3.9 Efficacy analysis

Efficacy analysis will be performed on the m-ITT, AT, and PPS datasets. The m-ITT dataset will be the primary analysis set for efficacy evaluation, while the AT and PPS datasets will serve as sensitivity analyses.

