### 3.10 Safety analysis

Safety analysis will be performed using the SS dataset.

All adverse events (AEs) reported during the clinical trial will be summarized. AEs will be coded using MedDRA and classified by SOC and PT. For incidence rate calculations, if a subject experiences multiple different AEs, they will be counted as one case for the overall incidence rate. If the same AE occurs multiple times in the same subject, the subject will still be counted as one case for the incidence calculation of that AE. For severity analysis, only the most severe occurrence of the same AE in a subject will be included. Additionally, if a subject experiences multiple AEs within the same SOC and PT, they will only be counted once for the incidence rate calculation within that SOC and PT.

The incidence, number of cases, and rate of all safety endpoints will be summarized. Exact Clopper-Pearson 95% CIs will be calculated for incidence rates. Group comparisons will use chi-square tests, continuity-corrected chi-square tests, or Fisher's exact test, as appropriate, with P-values reported. RD and RR with 95% CIs will also be calculated.

Mortality events will be analyzed using Kaplan-Meier methodology, with median survival time and 95% CIs reported. Kaplan-Meier survival curves will be plotted, and group comparisons will use the log-rank test with P-values reported.

A list of all AEs, serious AEs, adverse reactions, and serious adverse reactions (SS dataset) will be provided.

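### Safety is compared only by treatment actually received, and the SAP does not say where EVT-alone patients given IVT after failed EVT are counted

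*SAP*

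**What the plan says.** SAP 3.10 names one population: "Safety analysis will be performed using the SS dataset". This covers the group tests, risk differences and risk ratios for all safety endpoints. It also covers survival: "Mortality events will be analyzed using Kaplan-Meier methodology", with a log-rank comparison.

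SAP 3.2.2 sets the grouping. ITT, m-ITT and PPS follow the randomised arm, "while the AT and SS datasets will be analyzed based on the actual interventions received". SAP 3.1.5 defines membership: "The SS population includes all subjects who received either IVT followed by EVT or EVT alone treatment and had at least one safety follow-up". The AT set has the same members as m-ITT but "will be analyzed based on the actual treatment received" (SAP 3.1.3).

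The sets that keep the randomised groups have other uses. SAP 3.9 states "Efficacy analysis will be performed on the m-ITT, AT, and PPS datasets", and SAP 3.5 uses ITT for disposition and deviations. Protocol 10.2 defines no safety population and refers to the SAP.

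Protocol 5.3, repeated in Appendix 19, contains the rescue provision: "For patients in the EVT alone group who do not achieve successful reperfusion" within the 4.5-hour window and have not reached the rtPA maximum, "they may subsequently receive IVT with rtPA at a dose of 0.9 mg/kg". This post-EVT intravenous provision is written for the EVT-alone arm only.

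Neither document says where a patient who had EVT and then IVT is counted. SAP 3.2.2 leaves case-handling matters that the protocol does not describe to case discussions, and states no criteria or blinding for them.

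**The concern.** A main safety question is whether giving IVT before EVT adds bleeding or death. The plan answers it with a comparison that is not protected by randomisation. One route by which patients could change group is opened by a poor post-randomisation event, failed reperfusion, and exists in one arm only.

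The sequence EVT then IVT matches neither of the two treatment labels in SAP 3.1.5, so someone must decide where these patients go. In an open-label trial with no stated rule, that decision could be made after outcomes are known.

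Safety would weigh heavily if the trial moves to the non-inferiority question, where the practical issue is whether IVT can be omitted. A rescued patient who dies could also appear as mRS 6 under EVT alone in the primary analysis and as an IVT-group death in the safety table. The AT efficacy sensitivity analysis has the same gap.

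**Working it through.** **1. Arm size.** The plan's figure reproduces. With 42.03% against 26.14%, one-sided alpha 0.025 and 80% power, the unpooled formula is

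n = (1.960 + 0.842)² × (0.4203 × 0.5797 + 0.2614 × 0.7386) / 0.1589² = 135.8, so 136 per group, and 136 / 0.80 = 170.

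Only the 170 is used below.

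**2. Where an EVT-then-IVT patient could be counted**

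| Reading | Basis | Effect on EVT alone |
|---|---|---|
| With the IVT group | rtPA was actually given intravenously | loses failed-reperfusion patients |
| In neither group | the sequence matches neither label in SAP 3.1.5 | loses failed-reperfusion patients |
| Stays in EVT alone | IVT did not precede EVT, and Protocol 5.3 still calls these patients EVT-alone patients | none |

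No section selects one of these.

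**3. Size of the shift.** Take n = 170 per arm, the same true event risk q in both randomised arms, and k rescued EVT-alone patients with event risk r.

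- Moved to IVT: RD = (qn + kr)/(n + k) − (qn − kr)/(n − k) = 2nk(r − q)/(n² − k²)
- Left out: RD = q − (qn − kr)/(n − k) = k(r − q)/(n − k)
- Kept in EVT alone: RD = 0

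The sign follows r − q, so either regrouping counts against IVT whenever rescued patients fare worse than average.

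*Mortality, assuming q = 40% and r = 60%:*

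| k (share of arm) | Moved to IVT | Left out |
|---|---|---|
| 3 (about 2%) | 204/28,891 = 0.7 points | 0.6/167 = 0.4 |
| 5 (3%) | 340/28,875 = 1.2 | 1.0/165 = 0.6 |
| 10 (6%) | 680/28,800 = 2.4 | 2.0/160 = 1.3 |
| 17 (10%) | 1,156/28,611 = 4.0 | 3.4/153 = 2.2 |

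For k = 17 moved, r = 50% gives 578/28,611 = 2.0 points and r = 70% gives 1,734/28,611 = 6.1.

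*sICH, assuming q = 6% (10.2 events per arm) and r = 20%, moved to IVT:*

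- k = 5: 11.2/175 against 9.2/165, risk ratio 1.15, RD 0.8 points
- k = 10: 12.2/180 against 8.2/160, risk ratio 1.32, RD 1.7 points
- k = 17: 13.6/187 against 6.8/153, risk ratio 1.64, RD 2.8 points

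With r = 15%, k = 17 gives 520.2/28,611 = 1.8 points.

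**4. Chance of a false nominal finding.** This uses a different assumed baseline (q = 35%, r = 60%), a normal approximation and the SAP's two-sided 0.05 level. Rescue shares of 2%, 5% and 10%, all moved to IVT, give RDs of 1.0, 2.5 and 5.1 points. Nominal significance then occurs in 5.4%, 7.7% and 16.4% of trials instead of 5%.

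**5. Possible opposite shifts.** Read literally, SAP 3.1.5 may also exclude IVT-arm patients who never reach EVT, and early deaths without a safety follow-up. If j such patients leave the IVT arm with event risk r, its rate falls by j(r − q)/(n − j). With j = 5 and r = 60% that is 1.0/165 = 0.6 points in favour of IVT, which exactly cancels five rescued patients left out of EVT alone.

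**The case against.** As-treated grouping for safety is common and defensible, because it attributes bleeding to exposure. AT efficacy is declared a sensitivity analysis only. Both points stand, and they are reasons to keep the as-treated version as supportive. They do not supply the missing classification rule.

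A reader might infer that the plan, as written, transfers failed EVT-alone patients into the IVT group or drops them, and so makes IVT look more harmful. The documents do not support that much, for three reasons.

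- Keeping these patients in EVT alone is a natural reading, because the SAP label describes a sequence that they did not receive.
- Leaving them out is the weakest reading. SAP 3.1.2 defines m-ITT with the same two treatment labels, so a literal reading would remove them from the primary analysis too. Protocol 10.2 requires only that m-ITT patients were randomised and treated, which points to inclusion.
- The direction is conditional on rescued patients faring worse, and it concerns one route only. The exclusions in step 5 could offset it.

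Numbers may also be small, since rescue requires failed reperfusion, time left in the 4.5-hour window and remaining rtPA allowance. Finally, 90-day deaths are partly visible by randomised arm: SAP 3.2.3 scores them as mRS 6, and they enter the m-ITT bar chart and the ordinal shift analysis. That does not extend to sICH, new infarction, procedural complications or the log-rank test.

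**Conclusion.** The concern holds as a gap in specification. The only planned safety comparison is by treatment received, a foreseeable protocol-permitted pathway has no assigned group, and most safety endpoints have no randomised-arm version. The result can therefore depend on an unstated choice.

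The size is illustrative, because every event and rescue rate above is an assumption. The spurious mortality difference ranges from zero, if rescued patients stay in EVT alone, to about 4 points if 10% of the arm is moved at 60% mortality. At about 2% it is under 1 point. The net direction across all SS exclusions cannot be determined from the documents.

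This should be fixed, but it does not threaten the primary endpoint, the sample size or the superiority or non-inferiority decision, all of which rest on m-ITT by randomised arm.

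**What to change.** - In SAP 3.2.2 and 3.10, make the safety comparison by randomised group, in all randomised or m-ITT patients, the main analysis. Include the Kaplan-Meier and log-rank analysis. Keep the as-treated SS version as supportive.
- For AT and SS, define actual treatment by whether IVT started before EVT initiation, using the guiding-catheter time in Protocol 5.1. Rescue IVT given after EVT then stays in EVT alone for analysis.
- State where patients who received IVT but no EVT are counted, and how the safety follow-up condition treats very early deaths.
- List rescue-IVT patients and their events separately.
- Settle these rules before outcomes by arm are seen, and do not leave them to case discussions.

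The cost is SAP wording and one extra set of safety tables. Protocol 8.1.4 already records the route and time of thrombolysis and the time of EVT initiation. No patients or procedures are added, and no change to the clinical rescue rule is implied.

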### 3.2.3 Rules for handling missing data

Any requested data that is not provided will be considered as missing data.

Missing data will be displayed as “ ” in the listings. If data is recorded as “Not Applicable” (NA) or “Not Known” (NK), such data will appear in the listings as per their original record. However, for statistical analysis, they will be treated as missing data.

#### Handling of missing efficacy data

The primary efficacy analysis will be conducted based on the m-ITT population, and every subject must have a 90-day mRS score. If a subject dies before 90 days, they will not be considered missing and will be assigned the highest mRS score of 6 for evaluation. If the 90-day mRS value is missing but the subject's survival is confirmed within 90 days, the last available observation (e.g., from day 5 or discharge) will be carried forward to impute the missing value. For subjects with an unknown survival status at 90 days, the worst possible score (mRS = 6) will be assigned.

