8.3 Study procedures

Patients will undergo evaluations of vital signs, mRS, NIHSS, and GCS at baseline, 18–24 hours after procedure, 24–72 hours after procedure, and 5–7 days after stroke onset. These evaluations are also routine clinical practices and will be conducted by certified investigators.

At baseline, patients will undergo CT/CTA, MRI/MRA, or CT/DSA tests to assess infarct size, vascular lesion location and extent, and collateral circulation. During the EVT procedure, vascular recanalization, reperfusion, and new regional embolism will be evaluated, along with documentation of procedural details. At 24–72 hours after procedure, patients will undergo CT/CTA or MRI/MRA tests to evaluate infarct size, vascular recanalization, and

intracranial hemorrhage. At 5–7 days after stroke onset, patients will undergo a CT or MRI test to assess infarct size and intracranial hemorrhage.

Additionally, patients will undergo evaluations of mRS, BI, and EQ-5D-5L at 30±7 days and 90±14 days after stroke onset.

Detailed trial flowcharts and visit schedules are presented in **Appendices 16 and 17**.

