8.4 Withdrawal of individual participants

Participants can withdraw from the trial at any time and for any reason without any consequence. Investigators can also decide to withdraw a participant due to urgent medical reasons. Data from patients who do not provide consent for further participation will be anonymized and used for baseline analysis to better describe the study population. Missing data, including the final mRS score, will be addressed using statistical methods during analysis. Critical parts of personal data will be removed.

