10.1 Sample size calculation

Currently, no large-scale RCTs exist in this field. The sample size calculation for this study is based on the results of the RESCUE-RE registry study in the Chinese population^[25], which reported that the proportion of patients achieving a mRS score ≤ 2 at 90 \pm 14 days post-procedure was 42.03% in the IVT followed by EVT group and 26.14% in the EVT alone group. Based on the superiority hypothesis, the study aims to determine whether the favorable outcome rate (90-day mRS ≤ 2) in the IVT followed by EVT group is superior to that in the EVT alone group. Assuming a one-sided type I error rate of 0.025 and 80% statistical power, and using a 1:1 randomization ratio, the required sample size is 136 patients per group (a total of 272 patients). Considering an anticipated dropout rate of approximately 20%, the final sample size is adjusted to 340 patients, with 170 patients per group.

This study hypothesizes that IVT followed by EVT is superior to EVT alone. However, given the limited reference data and clinical evidence in the anterior circulation indicating that EVT alone may be non-inferior to IVT followed by EVT, an interim analysis is planned after one-third (114) of the patients have completed follow-up for the primary endpoint. During the interim analysis, the DSMB will evaluate the efficacy data from both groups and conduct a sample size re-estimation based on the conditional power calculated from the available data. The DSMB will provide recommendations to the BEST-BAO research team on adjustments to the sample size or modifications to the study hypothesis.

If the efficacy advantage of the IVT followed by EVT group over the EVT alone group is less than anticipated, the sample size may be expanded appropriately, with an upper limit of no more than 20% of the original sample size. If the efficacy of the two groups appears to be similar, the study design will shift to a non-inferiority framework, evaluating whether EVT alone is non-inferior to IVT followed by EVT. Assuming similar efficacy (with both groups achieving a 90-day mRS score ≤ 2 in 42.03% of patients), the current sample size of 170 patients per group provides 80% power to test non-inferiority, with a one-sided type I error rate of 0.025 and a non-inferiority margin of -15%. The interim analysis and sample size re-estimation will be conducted under the strict control of the DSMB to ensure that the type I error rate is not inflated.

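### The single rule for a missing 90-day mRS can inflate the false non-inferiority rate, and no planned sensitivity analysis varies it

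*SAP*

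**What the plan says.** SAP 3.2.3 (Handling of missing efficacy data) applies to the primary m-ITT analysis and treats three cases:

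- A patient who dies before day 90 is scored mRS 6 and is not regarded as missing.
- For a patient known to be alive without a 90-day score, "the last available observation (e.g., from day 5 or discharge) will be carried forward to impute the missing value".
- A patient about whom it is not known whether they were alive at day 90 is treated like a death: "the worst possible score (mRS = 6) will be assigned".

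Protocol 8.4 names no method: "Missing data, including the final mRS score, will be addressed using statistical methods during analysis".

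SAP 3.9.1 tests superiority or, if the hypothesis is switched after the interim analysis, non-inferiority with a 15-point margin. It provides no different missing-data rule for the second case. The sensitivity analyses in SAP 3.9 and 3.9.1 are the as-treated set, the per-protocol set, and local instead of central mRS.

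On the amount of missing data, Protocol 10.1 gives only a general allowance: "Considering an anticipated dropout rate of approximately 20" per cent. Protocol 8.3 schedules a later score that can be carried forward: "patients will undergo evaluations of mRS, BI, and EQ-5D-5L at 30±7 days and 90±14 days after stroke onset".

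**The concern.** A score of 6 is always a failure on mRS ≤ 2, and an early score can miss later recovery. Each true success that the rule records as a failure lowers that arm's observed success rate. If this happens to a similar extent in both arms, both rates are multiplied by about the same factor below 1, and so is their difference.

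A difference pulled toward zero makes superiority harder to show, so there the rule errs on the safe side. In the non-inferiority test it makes a real loss look smaller than it is, and the lower confidence limit clears the margin more often than it should. A trial that may switch framework at the interim therefore carries a rule that is cautious in one framework and permissive in the other. Because none of the planned sensitivity analyses changes the rule, the report would not show whether a non-inferiority claim depended on it.

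**Working it through.** **Inputs from the documents** (Protocol 10.1; SAP 1.5 and 3.9.1): success rates "42.03% in the IVT followed by EVT group and 26.14% in the EVT alone group"; one-sided alpha 0.025; 136 per arm before and 170 per arm after the dropout allowance; margin 15 points.

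**Assumed, because the documents do not give them:** m, the share of 90-day mRS that is missing (5% to 20%); k, the share of true successes among missing patients that the rule still scores as successes (0 to 0.8); missing patients have the same true success rate as the rest of their arm; the rule does not turn true failures into successes. The calculation uses the unadjusted risk difference with an unpooled normal approximation, whereas the SAP decides on an adjusted one.

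**The plan's own figures.**
- Superiority: n = [0.4203 × 0.5797 + 0.2614 × 0.7386] × (1.960 + 0.842)² / 0.1589² = 135.8, so 136 per arm; 136 / 0.8 = 170.
- Non-inferiority: n = 2 × 0.4203 × 0.5797 × (1.960 + 0.842)² / 0.15² = 170.0, so 170 per arm gives 80%.

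Both are reproduced.

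**False non-inferiority rate.** Take the stated aim (EVT alone against IVT followed by EVT) and a true loss of exactly 15 points: 42.03% against 27.03%. With d = 1 − m(1 − k), the observed rates are q_I = 0.4203d and q_E = 0.2703d. Then

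rate = Φ[(q_E − q_I + 0.15)/SE − 1.96], with SE = √[q_I(1 − q_I)/170 + q_E(1 − q_E)/170].

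With nothing missing this returns 2.5%. With all missing scored as failures (k = 0):
- m = 5%: 0.3993 and 0.2568, difference −14.25 points, SE 0.0503; Φ(−1.811) = 3.5%.
- m = 10%: 0.3783 and 0.2433, difference −13.5 points, SE 0.0497; Φ(−1.658) = 4.9%.
- m = 20%: 0.3362 and 0.2162, difference −12.0 points, SE 0.0481; Φ(−1.336) = 9.1%.

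A simulation of this case (400,000 runs) gave 2.6%, 3.4%, 4.9% and 9.1% at 0, 5, 10 and 20% missing.

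| True successes kept (k) | 5% missing | 10% missing | 20% missing |
|---|---|---|---|
| 0 | 3.5% | 4.9% | 9.1% |
| 0.25 | 3.2% | 4.1% | 6.7% |
| 0.5 | 3.0% | 3.5% | 4.9% |
| 0.8 | 2.7% | 2.9% | 3.3% |

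**Unequal missingness** (k = 0, same true loss):
- 10% in IVT followed by EVT, 5% in EVT alone: 0.3783 and 0.2568, difference −12.1 points, rate 8.2%.
- 5% and 10%: 0.3993 and 0.2433, difference −15.6 points, rate 1.9%.

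**Superiority power** at the registry rates, 170 per arm, k = 0: Φ[0.1589(1 − m)/SE − 1.96] = 85.4% at 5% missing, 82.5% at 10% and 76% at 20% (difference 12.71 points). With 136 evaluable per arm and no imputation it is 80%.

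**The case against.** Several stronger readings are tempting, and the documents do not support them.

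- **That most missing patients become failures because of the rule.** Neither an early mRS distribution nor the split between known alive and unknown status is given. At the planning rates about 58% to 74% would be failures anyway; only true successes scored as failures cause bias.
- **That survivors are frozen at a first-week score.** Day 5 and discharge are examples. The rule takes the last available score, and one is scheduled at day 30. Likewise, a living patient who withdraws is scored dead only if survival status is unknown.
- **That any true difference shrinks.** This needs similar missingness by arm. Treatment is open-label, so missingness may differ, and more missing data in the EVT-alone arm widens the difference.
- **That superiority power is generally below 80%.** It is above 80% at 5% and 10% missing, and falls to 76% only at 20% missing with everything scored as failure.
- **That 20% forecasts missing mRS.** It is a general dropout allowance. Untreated patients leave the m-ITT set and are not imputed. If, as an assumption, half of the dropout were untreated (153 analysed per arm, 17 imputed), the all-failure rate would be 5.0%. Telephone and proxy interviews (Protocol 8.1.5), and local scores where central ones are missing (SAP 3.9.1), also limit missingness.

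Multiple imputation also has a weakness: it assumes data are missing at random, which is doubtful for patients lost with unknown survival.

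These points limit the size of the problem. They do not remove the direction of the bias under similar missingness or the absence of any analysis that would reveal it. Possible imbalance between the arms makes such an analysis more necessary.

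**Conclusion.** The point holds in conditional form. If missingness is similar in the two arms, the rule biases the risk difference toward zero and raises the false non-inferiority rate above 2.5%. The excess is small at 5% missing (2.7% to 3.5%), moderate at 10% (2.9% to 4.9%) and potentially large at 20% (3.3% to 9.1%). The 9.1% is the upper end of the equal-missingness range: it needs the whole dropout allowance to be missing 90-day scores inside the m-ITT set and no true success to be kept. With unequal missingness the error can be higher or lower than nominal.

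For superiority the rule is conservative under the same condition and is not a threat to validity.

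These are error rates of the non-inferiority test itself; they do not model the interim decision that leads to it. SAP 1.5 and 3.9.1 define p_T as the IVT-followed-by-EVT arm, so the written non-inferiority hypothesis runs opposite to the stated aim. The shrinkage argument applies in either direction.

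**What to change.** Amend SAP 3.2.3 and 3.9.1 before the final data are unblinded. For any non-inferiority conclusion:

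- Analyse the primary endpoint with multiple imputation, done separately by arm, for patients not confirmed dead. Use the baseline covariates and the 24–72 h, 5–7 day and 30-day mRS.
- Keep mRS 6 for confirmed deaths only.
- Report the current carry-forward and worst-score rule as a sensitivity analysis.
- Require a tipping-point analysis in which the assumed success rates among missing patients can differ between the arms.

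At a minimum, leave the current rule as primary but add the multiple-imputation and tipping-point analyses as sensitivity analyses that must support a non-inferiority claim.

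The cost is an SAP amendment and modest programming, with no new data and no more patients. The downside is the missing-at-random assumption, which the tipping-point analysis is there to test.
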